-------------------------	---

ASTRO Standalone Study Schema

¹Enrollment estimates reflect pooled enrollment of the ASTRO Standalone Study (PH601) and the ASTRO Nested Substudy within TERBO BRAIN (PH600).

2. ASTRO Standalone Study Introduction

Individuals who are living with PHIV and PHEU have been found to have increased adiposity [132, 133], insulin resistance [134, 135], dyslipidemia [136, 137], and inflammation [138-140], likely due to the interplay of chronic infection, antiretroviral therapy (ART), and effects on fetal programming. In the general population, increased aortic stiffness is an early consequence of metabolic dysfunction and immune activation that results in excess transmission of pulsatile pressure to the microvasculature with resultant end-organ damage [141]. As a low-resistance organ, the brain is particularly vulnerable to pressure and pulsatility induced by increased arterial stiffness [142], which in turn has been linked to neurocognitive impairment [143, 144]. Nonetheless, whether aortic stiffness is increased or contributes uniquely to the pathogenesis of multi-systemic comorbidities in individuals with PHIV and PHEU remains a critical gap in knowledge. This standalone study will investigate aortic stiffness and its contribution to end-organ damage in young adults born to mothers with HIV. The central hypothesis of this study is that the abnormal metabolic and pro-inflammatory milieu in individuals with PHIV and PHEU will promote aortic stiffness, which in turn will predispose to altered neurocognitive function as a key indicator of end-organ damage. To test this hypothesis, carotid-femoral pulse wave velocity (cfPWV) will be ascertained among participants as a low-cost and reproducible index of aortic stiffness. First, differences in aortic stiffness between those living with PHIV and PHEU, as well as similar-age individuals from the general population, will be investigated. Furthermore, associations of metabolic and inflammatory parameters with aortic stiffness will be assessed in people with PHIV and PHEU to uncover novel mechanisms of aortic dysfunction. Second, the role of aortic stiffness in the pathogenesis of altered neurocognitive function in those with PHIV and PHEU will be delineated by assessing relationships of cfPWV with neurocognitive outcomes measured in AMP Up. This study could uncover increased aortic stiffness as an as-yet unrecognized sequela of perinatal HIV infection and in utero HIV exposure that may serve as a harbinger for adverse health outcomes. Moreover, this pilot study will inform the development of targeted interventions to attenuate aortic stiffness as an early and modifiable risk factor in these populations.

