2.2 Rationale

In the general population, aortic stiffness is an early sequela of metabolic dysfunction and immune activation that predisposes to multi-systemic morbidity including cardiac, renal, and neurologic disease [142-144, 149]. While those living with PHIV and PHEU have a high prevalence of traditional cardiovascular disease risk factors [133, 145, 147, 170] and immune abnormalities [138, 140, 148], the integrity of the large arterial system in these individuals has not been previously well evaluated in comparison to individuals from the general population. Nonetheless, we have previously shown that youth with PHIV in South Africa have endothelial dysfunction of the microvasculature [171, 172]. Furthermore, in a prior PHACS analysis, children with PHIV were found to have higher circulating biomarkers of endothelial dysfunction vs. controls in association with greater abdominal adiposity and HIV infection severity [173]. As endothelial dysfunction is intimately tied to abnormalities in aortic stiffness [149, 174], these data stress the urgency to further delineate the vascular phenotype among those with PHIV and PHEU within PHACS. Consistent with the mission of PHACS to improve the lives of people with PHIV and PHEU, the findings from this study may illuminate carotid-femoral pulse wave velocity (cfPWV, a measure of aortic stiffness) as a simple and noninvasive tool to identify individuals who are at high risk of chronic comorbidities and thus require intensive long-term monitoring. Moreover, this pilot study will inform the development of targeted interventions to attenuate aortic stiffness as an early and modifiable risk factor in these populations, which can be further explored in future work.

3 Aims and Hypotheses

The ASTRO Standalone Study will investigate aortic stiffness and its contribution to end-organ damage among young adults (22-29 years old) born to mothers with HIV.

3.1 Aim 1

To investigate the impact of in utero HIV exposure and perinatal HIV infection on aortic stiffness in young adults.

Hypotheses:

- 1a: Young adults with perinatal HIV infection (YAPHIV) will have the highest aortic stiffness, followed by young adults with perinatal HIV exposure without infection (YAPHEU), followed by similar-age individuals from the general population.
- 1b: In YAPHIV and YAPHEU, alterations in traditional cardiovascular risk factors, immune markers, and pro-inflammatory eicosanoids will be associated with higher aortic stiffness.

3.2 Aim 2

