
To evaluate the role of aortic stiffness in the pathogenesis of neurocognitive dysfunction in individuals with PHIV and PHEU.

Hypotheses:

Among YAPHIV and YAPHEU, higher aortic stiffness will be associated with worse neurocognitive outcomes, particularly in global cognition, executive function, and memory.

4. Study Design

The ASTRO Standalone Study is a cross-sectional study that will evaluate differences in aortic stiffness among young adults (22-29 years old) in YAPHIV and YAPHEU, and similar-age individuals from the general population ($n \approx 450$). Participants in the ASTRO standalone study will be pooled for analysis with participants in the ASTRO Nested Substudy of the TERBO BRAIN study (PH600) for a total of approximately 50 YAPHIV and 50 YAPHEU. Participants from AMP Up who consent to enroll in the ASTRO Standalone Study will undergo several brief procedures at a single time point. Furthermore, their data collected in AMP Up will be incorporated into study analyses to address novel research questions, which in turn will maximize the insights to be gained from existing efforts in PHACS.

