7.5.1 Metabolic and Immune Serologic Markers

Fasting blood will be drawn for plasma glucose and serum insulin and lipids. Glucose and insulin will be used to calculate HOMA-IR as a measure of insulin resistance [229]. Serum high-sensitivity CRP [230, 231], plasma soluble CD163 (sCD163) [232, 233], and soluble CD14 (sCD14) [234, 235], also will be measured as key immune markers that have been shown to be elevated in both cardiovascular disease and HIV infection. CD4 T cell count and HIV viral load in YAPHIV participants will be ascertained from AMP Up as measures of HIV infection severity. HIV viral load and CD4 T cell count also will be drawn if not available within the past 3 months from AMP Up or routine clinical care.

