14.2 Statistical Analyses

Analyses described below are for pooled data from the ASTRO Standalone Study and the ASTRO Nested Substudy.

14.2.1 Aim 1: To investigate the impact of in utero HIV exposure and perinatal HIV infection on aortic stiffness in young adults

In Aim 1, differences in cfPWV between groups will be assessed, and relationships of cfPWV with metabolic and inflammatory parameters within each group will be examined. YAPHIV ($n \approx 50$), YAPHEU ($n \approx 50$), and young adults from the general population ($n \approx 450$) will be compared.

To minimize differences between groups, the general population sample will be standardized to the combined group of YAPHIV and YAPHEU on key covariates using probability weighting [289]. A propensity score for each participant will be obtained using a logistic regression model with study group (combined YAPHIV and YAPHEU, general population) treated as the outcome and rounded age, sex, race, and BMI treated as predictors. All YAPHEU and YAPHIV will be given a weight of 1, whereas the weight for each individual in the general population will be defined as (propensity score)/(1 - propensity score). A sensitivity analysis in which the general population sample is standardized to YAPHIV or YAPHEU individually and compared to each group in separate analyses will also be performed.

For analyses, variables that are not normally distributed and right-skewed will be log-transformed to approximate a normal distribution. **Hypothesis 1a:** The distribution of sociodemographic and clinical variables (including cfPWV) will be described across study groups using the mean (standard deviation, SD) and frequency, as appropriate, before and after weighting. To compare cfPWV between groups, unadjusted and adjusted linear regression models with weighting will be fit using generalized estimating equations (GEE) to obtain the robust variance estimator. The average difference (95% confidence interval, CI) will be reported for each pair of groups. The basic adjusted model will include age, sex, race, and potential confounders (e.g., primary caregiver education [290-292], adverse childhood experiences [293-295], and physical activity [296-298]). Analyses stratified by sex and obesity will also be performed to evaluate qualitatively whether differences in cfPWV between groups differ by strata, acknowledging that these analyses will have limited power.

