In Aim 2, relationships of aortic stiffness with neurocognitive measures within YAPHIV and YAPHEU will be interrogated. Each group will be analyzed separately. Descriptive summaries will be prepared using the same approach described in Aim 1. Unadjusted and adjusted linear regression models will be fitted using GEE to assess associations between cfPWV and each neurocognitive parameter. A basic model will adjust for age, sex, race, and potential confounders (as listed in Aim 1). Analyses will be stratified by sex, obesity, and CRP to determine if key relationships differ by strata, acknowledging that these analyses will have limited power.

Power calculations. There is 80% power to detect a correlation of at least $r = 0.38$ within YAPHEU and YAPHIV unadjusted and a slightly higher correlation when adjusted ($\alpha = 0.05$).

Expected Outcomes. In YAPHIV and YAPHEU, cfPWV also will inversely relate to neurocognitive outcomes (e.g., Executive Function, Episodic/Working Memory, Fluid Cognition; NIH Toolbox).

15. Human Subjects

The ASTRO Standalone Study will be conducted in compliance with the protocol, International Council for Harmonisation of Technical Requirements for Pharmaceuticals for Human Use (ICH) GCP guidelines, and 45 CFR §46.

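### Aim 2 asks about the role of stiffness, but its one stated adjusted model names none of the metabolic and immune factors that the protocol places upstream of stiffness

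*Protocol*

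**What the plan says.** Section 3.2 and the heading of Section 14.2.2 give the aim: "To evaluate the role of aortic stiffness in the pathogenesis of neurocognitive dysfunction in individuals with PHIV and PHEU". The hypothesis under it is worded as an association between higher stiffness and worse cognition. The Introduction (Section 2) describes the open question more strongly, as "whether aortic stiffness is increased or contributes uniquely to the pathogenesis of multi-systemic comorbidities in individuals with PHIV and PHEU".

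The analysis in Section 14.2.2 is run separately in each group: "Unadjusted and adjusted linear regression models will be fitted using GEE to assess associations between cfPWV and each neurocognitive parameter". On covariates it says "A basic model will adjust for age, sex, race, and potential confounders (as listed in Aim 1". The list it points to, in Section 14.2.1, reads "potential confounders (e.g., primary caregiver education [290-292], adverse childhood experiences [293-295], and physical activity [296-298".

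Sections 2 and 2.1 place metabolic dysfunction and inflammation upstream of stiffness. Hypothesis 1b (Section 3.1) carries this into the study groups: "alterations in traditional cardiovascular risk factors, immune markers, and pro-inflammatory eicosanoids will be associated with higher aortic stiffness". The variables are planned for collection: weight, height, waist and hip in Section 7.2; lipids, hs-CRP, sCD163 and sCD14 in Section 7.5.1, where also "Glucose and insulin will be used to calculate HOMA-IR as a measure of insulin resistance".

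In Aim 2, obesity and CRP appear only as stratifying variables, to see whether relationships differ between strata, with limited power acknowledged. The other markers are not mentioned there.

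**The concern.** The covariates were chosen for a different purpose: comparing cfPWV between exposure groups. For the cfPWV-cognition question the relevant confounders are the common causes of stiffness and cognition. The protocol itself supplies candidates for one half of that, since it holds that adiposity, insulin resistance and immune activation drive stiffness. If any of them also affects cognition other than through the aorta, part or all of the basic-model coefficient reflects that factor.

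What is at stake is interpretation. Sections 2, 2.1 and 2.2 intend cfPWV to serve as a marker of people at high risk and as a modifiable target for intervention. An association due to shared causes could still support the first use, but not the second.

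**Working it through.** **Inputs from the protocol.** About 50 per group (Section 14.1.1); alpha 0.05 and a detectable correlation of 0.38 at 80% power (Section 14.2.2). Two-sided testing is stated for the Aim 1 group comparison and is assumed here for Aim 2.

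**The plan's own figure.** Fisher z: r = tanh[(1.960 + 0.842)/√(50 − 3)] = tanh(0.409) = 0.387. Power at r = 0.38 is 0.78 by Fisher z and 0.79 by simulating the t-test. The figure reproduces and is not in dispute.

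**Assumptions, not in the documents.** One standardised factor M has correlation a with cfPWV and −b with cognition. cfPWV has no direct effect on cognition. The basic model has six or eight other covariates, independent of M.

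**Induced correlation.** r = −ab, so in size 0.30² = 0.09, 0.38² = 0.144 and 0.50² = 0.25. For M alone to induce the 0.38 the study is powered for, both links would need to be about 0.62 (0.62² = 0.384).

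**Rejection rate by formula.** With six covariates the Fisher z statistic has mean atanh(ab) × √(50 − 3 − 6) = atanh(ab) × 6.40. At a = b = 0.50 this is 0.255 × 6.40 = 1.64, and the probability of exceeding 1.96 is 37%. The same step gives 15% at 0.38 and 9% at 0.30.

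**Rejection rate by simulation**, n = 50, per outcome and per group:

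| a, b | Covariates | Basic model | M added |
|---|---|---|---|
| 0.30, 0.30 | 8 (two runs) | 8.9%, 8.0% | 5.0%, 5.0% |
| 0.30, 0.30 | 6 | 9.1% | 5.1% |
| 0.38, 0.30 | 8 (two runs) | 11.3%, 11.1% | 5.0%, 5.6% |
| 0.38, 0.38 | 8 (two runs) | 14.9%, 14.7% | 4.9%, 4.7% |
| 0.50, 0.50 | 8 (two runs) | 35.1%, 37.4% | 5.2%, 5.5% |
| 0.50, 0.50 | 6 | 38.2% | 4.7% |

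**Sensitivity.**
- If the basic covariates explain 25% of M (assumed), the rates at 0.30, 0.38 and 0.50 fall to about 7%, 10% and 24%. If they explain 50%, the rates are about 6%, 8% and 15%.
- With two independent shared causes, each linked at 0.38, and only one of them adjusted for, rejection stays at about 18%.

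**Price of adjustment.** Take a true direct effect of 0.40 SD per SD and a score correlated 0.38 with cfPWV. Adding the score multiplies the coefficient's variance by about 1/(1 − 0.38²) = 1.17, and simulated power falls from 76% to 69%. Three separate variables, each correlated 0.38 with cfPWV and 0.2-0.5 with each other (assumed), bring it to about 57-64%.

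**The case against.** The hypothesis, the analysis text and the expected outcome for Aim 2 all speak of association, and the model fits that wording. The phrase about a unique contribution is one background sentence on comorbidities in general, not an estimand. The confounder list is given as examples and the model is called basic, so a fuller one is not excluded; an SAP, not shown here, may contain it. All this stands, and it confines the point to the gap between the aim as worded and the only adjusted model stated for it.

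A reader might infer that Aim 2 tests merely whether cfPWV and cognition are related at all. The text does not support that: age, sex, race and named social and activity factors are held fixed. Nor do the documents show that a positive result would be spurious, because they give no factor-cognition correlation. The 0.38 used above is the plan's detection limit, not an expected value.

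Stratifying by obesity and CRP does give some control. It is coarse, covers two of the factors, splits a group of about 50 and is aimed at effect modification.

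Over-adjustment is a fair worry for blood pressure, since Section 2.1 describes the link between stiffness and hypertension as running both ways. For adiposity, insulin resistance and immune activation it is weaker: the protocol puts them before stiffness, so they are not mediators of its effect on cognition. Even so, the blood markers come from the study visit, whereas under Section 5.1 the standalone participants' cognition may have been tested up to two years earlier. A later marker value is an imperfect stand-in for an upstream cause.

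**Conclusion.** The point holds in limited form. The stated Aim 2 model cannot separate a contribution of stiffness from a metabolic or immune cause shared with cognition, although the protocol names such factors as causes of stiffness and plans to measure them. With independent covariates, the false-positive rate per test would be about 8-9% at shared links of 0.30, 15% at 0.38 and 35-38% at 0.50. It would be lower where the basic covariates already carry part of the factor. These sizes rest entirely on the assumed links.

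It would go too far to infer that one further model would establish a unique contribution. The return to 5% in the simulation follows from adjusting for the only confounder that was built in. Residual confounding, the cross-sectional design and the timing of cognitive testing remain. This is a worthwhile, inexpensive improvement, not an error that invalidates the aim.

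**What to change.** In Section 14.2.2, keep the basic model and add a prespecified secondary model for each neurocognitive outcome that also includes adiposity and the metabolic and immune markers. With about 50 per group, one summary score is preferable to several separate terms. Leave blood pressure out of the score for the reason given above. In YAPHIV, consider adding HIV severity (CD4 count and viral load), which is also collected.

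State that the basic estimate is reported as an association. State too that anything said about a role of stiffness is interpreted in light of the further-adjusted model, with the remaining limitations noted.

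The cost is a few sentences and one more model per outcome and group, using variables already planned, plus the loss of power shown above. That loss is the reason to prefer one score over three terms.

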15.1 Participant Confidentiality

All participants enrolled in the PHACS Network are assigned unique PHACS PID and SID (PIN) numbers as described in [Section 7.6](#). All participants co-enrolled in a PHACS study will use the same PHACS PID number assigned for their first PHACS study. The PID and SID (PIN) numbers will be used for identification purposes on all laboratory specimens, evaluation forms, and reports retained in the research records and generated in the PHACS central database, as well as for online assessments such as the online survey. A list linking the participant names with the PID and SID (PIN) numbers will be stored at the clinical site under double locks, separate from all other research records. All research records will be stored in a secured area in locked files.

All PHACS investigators and research staff persons at the clinical sites are required to sign non-disclosure forms pledging to hold research information in confidence. All collaborators seeking PHACS data are required to sign DUAs as described in Section 12.4.

Research staff will work with participants and/or their legal guardians to record contact information, which may also include the names and contact information of people (friends, family, or others) who may always know the whereabouts of participants. Establishing this list is a voluntary exercise and, if used in the event contact is lost with a participant, only a previously agreed to level of information will be disclosed. When contact is re-established with participants who were lost, willingness to continue study participation will be first ascertained.

15.2 Certificate of Confidentiality

As an NIH-funded project using identifiable, sensitive information, the ASTRO Standalone Study is automatically covered by a Certificate of Confidentiality issued from the DHHS. With this Certificate in place, the ASTRO researchers cannot be forced to turn over identifying information about a study participant in any Federal, State, or local criminal, administrative, legislative, or other proceedings. This Certificate does not prevent a study participant from volunteering to turn over their research information nor does it prevent investigators from providing research-related information to others when requested by the study participant or when required by law such as in cases of suspected or actual harm to or by the study participant.

The clinical site PI will make study documents (e.g., ICFs, CRFs) and pertinent records available for inspection by the local IRB, the HLC IRB, the PHACS site monitors, the NIH, the OHRP, or the sponsor's designee for confirmation of the study data as needed.

15.3 Risks and Benefits

15.3.1 Risks Associated with Participation

Participation in this study poses no more harms or discomforts to research participants than they may experience in normal daily life or during routine medical tests. Possible risks resulting from this study include the following:

- Measurement of aortic stiffness with SphygmoCor may cause mild discomfort or anxiety as it is an unfamiliar procedure. The procedure will be explained to put the participant at ease.
- Venipuncture to collect blood specimens may cause local discomfort, bleeding, or bruising; rarely a small clot or infection can occur at the blood draw site.
- Fasting is required for 8 hours prior to blood draw and should present little risk. Some participants may feel hunger, irritability, and lightheadedness as a result of fasting.
- There are no risks associated with vital signs or anthropometric evaluation.
- The evaluations that are involved in this study require answering questions about stressful or traumatic events and lifestyle behaviors. Some of the questions may make participants feel distressed or uncomfortable, and they may decline to respond. As the members of the research team have specific and extensive training in dealing with risks of this kind, no additional difficulties are expected beyond those experienced in a typical clinical practice. The PHACS Emergency Protocol provide specific guidance to site staff to address atypical and/or worrisome emotional responses that may occur during a study visit. The online survey tool is designed to reduce the discomfort that some participants may experience in self-reporting some behaviors and increase the likelihood of accurate responses. Despite the multiple measures taken to protect participant confidentiality, web-based communications may be at risk for hacking, intrusions, and other violations.
- While multiple safeguards are in place to protect participant privacy and confidentiality, a participant's health information may be inadvertently disclosed. Research staff members are required to complete human subjects research training and will be trained on protecting participant/caregiver confidentiality in the ASTRO Standalone Study.

